#### **4.6 Laboratory testing**

The dried blood spots will be used to conduct multiplex serological assays on the Luminex platform to look for antibodies to Treponemes and other infectious diseases. By measuring levels of anti-Treponemal antibodies in children we will be able to estimate the number of latent yaws cases within the community. We will choose a panel of infectious diseases that we know, or suspect, to be endemic in our populations and measure antibody responses specific to these pathogens in order to indicate exposure and seroprevalence at the individual, community and district level .

#### **4.7 Follow-up**

All samples for the primary analysis are collected at the first visit and therefore we do not anticipate loss to follow-up or non-compliance to be an issue. All individuals with a clinically suspected yaws lesion or ulcer, regardless of screening-assay result, will be offered treatment with azithromycin or referred to the relevant services for treatment in line with national guidelines. If other skin conditions are seen, participants will also be referred to the relevant services. As per WHO guidance, we will review patients with suspected yaws lesions at week four, when unhealed lesions will be swabbed and treatment with benzathine benzylpenicillin offered. If azithromycin resistance is detected through the laboratory analysis at any point during the study, we will work with yaws eradication programmes to implement interventions for study participants and communities.

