## 8 SAFETY CONSIDERATION AND REPORTING

### 8.1 Potential risks

Risks associated with participation in this study are minimal. Swabs are non-invasive and are routinely used programmatically. Finger prick blood samples may cause slight discomfort and bruising; however, these too are routinely used programmatically. Loss of privacy is a potential risk associated with participation in any research project. In this study, it is necessary to confirm cure at four weeks post-treatment, as per WHO guidelines, so it is essential personal details are recorded at the time of recruitment. Potential for loss of confidentiality will be minimized by use of coded study numbers on data collection forms and laboratory samples, and all data will be stored in locked filing cabinets and on encrypted, password-protected computer files. As with the use of any antibiotic, there is a risk that resistance may evolve in either TPE, *H. ducreyi* or in a host's commensal microbiota. There have also been reports of microbial gut community disturbances with azithromycin administration which could have long term implications. However, the data suggest that azithromycin antimicrobial resistance is not long-lived.

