## **8.2 Known potential benefits**

All individuals with a skin ulcer will be referred to relevant health services for treatment with azithromycin, regardless of screening-assay result, as this is an effective treatment for both *T. pallidum* and *H. ducreyi*. Due to the activity of azithromycin against a broad range of bacterial pathogens there is likely to be collateral benefits to taking the prescribed dose of azithromycin for yaws, as has been shown previously. By conducting this study we hope to improve in-country capacity for running field and laboratory studies. If the LAMP tests are shown to be an effective tool each country will have the capacity to use the assay in future studies and eradication campaigns.

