### **8.3.1 Definitions**

- I. Adverse event (AE): Any untoward medical occurrence in a patient or study participant, which occurs between enrolment and follow up (four weeks post enrolment).
- II. Serious adverse event (SAE): Any untoward medical occurrence that:
  - results in death;
  - is life-threatening;
  - requires inpatient hospitalization or prolongation of existing hospitalization;
  - results in persistent or significant disability/incapacity;
  - consists of a congenital anomaly or birth defect.

Serious adverse events are only likely to occur in participants with a severe allergy to penicillin; anyone requiring penicillin treatment will have their history checked. SAEs are rarely associated with azithromycin.

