## **8.4 Follow-up**

No formal study follow-up is planned for participants after the completion of study activities, however, as mentioned in section 5.6, participants will be re-visited four weeks after initial treatment and offered benzathine benzylpenicillin if treatment failure is thought to have occurred.

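### The week-four visit has two different starting points, and penicillin is first offered as the adverse-event window closes or after it has closed

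*Combined protocol and SAP*

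**What the plan says.** Five places in the protocol bear on the visit.

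- Section 4.7, on initial treatment: people with a suspected lesion "will be offered treatment with azithromycin or referred to the relevant services for treatment in line with national guidelines". No deadline for taking the drug is given.
- Section 4.7, on the visit: "we will review patients with suspected yaws lesions at week four, when unhealed lesions will be swabbed and treatment with benzathine benzylpenicillin offered". The starting point of the four weeks is not stated.
- Section 8.1: "it is necessary to confirm cure at four weeks post-treatment, as per WHO guidelines".
- Section 8.2 mentions referral only: "All individuals with a skin ulcer will be referred to relevant health services for treatment with azithromycin".
- Section 8.4: "participants will be re-visited four weeks after initial treatment and offered benzathine benzylpenicillin if treatment failure is thought to have occurred". It cites section 5.6 for this visit, but 5.6 covers laboratory quality assurance; the visit is described in 4.7. Section 8.4 also says that no formal follow-up takes place once study activities are complete.

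On safety, section 8.3.1 defines an AE as an untoward occurrence "which occurs between enrolment and follow up (four weeks post enrolment". It then says: "Serious adverse events are only likely to occur in participants with a severe allergy to penicillin", and adds that the history of anyone needing penicillin will be checked. The serious adverse event (SAE) definition states no time limits of its own.

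**The concern.** Two problems follow from the wording.

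**Safety capture.** Penicillin is the drug from which the protocol itself expects the rare serious reaction. In the protocol text it is first offered at the week-four visit, and that visit marks the end of the AE window. A site that applies the definition as written would not count a reaction on the following day as an AE. If the visit is timed from a delayed azithromycin dose, even an immediate reaction falls outside the stated four weeks.

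**The treatment decision.** Section 4.7 triggers the penicillin offer on an unhealed lesion; 8.4 requires suspected treatment failure. These match for someone treated about four weeks earlier. They do not match for someone who was referred and never took azithromycin: that lesion may be unhealed, but no treatment has failed. Sites in three countries could reasonably follow either section.

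**Working it through.** The plan gives no figure to reproduce. The check compares the starting points and then does day arithmetic.

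**Step 1. Starting points, side by side.**

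| Section | Four weeks counted from |
|---|---|
| 4.7 | not stated |
| 8.1 | treatment |
| 8.4 | initial treatment |
| 8.3.1 (end of AE window) | enrolment |

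**Step 2. When do they agree?** Let d be the number of days from enrolment to taking azithromycin. The AE window closes on day 28. A visit timed from enrolment falls on day 28; a visit timed from treatment falls on day 28 + d. The two coincide only when d = 0. Referral (4.7, 8.2) permits d > 0, or no dose at all.

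**Step 3. AE window left after an injection at the visit.** The documents give no value for d, so the values below are illustrative assumptions.

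- Visit timed from enrolment: 28 − 28 = 0 days left, whatever d is.
- Visit timed from treatment: 28 − (28 + d) = −d days.

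| d (days) | Visit day if timed from treatment | AE days left after injection | Days since azithromycin if the visit is instead on day 28 (28 − d) |
|---|---|---|---|
| 0 | 28 | 0 | 28 |
| 3 | 31 | −3 | 25 |
| 7 | 35 | −7 | 21 |
| 14 | 42 | −14 | 14 |

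On the most generous reading, the AE window closes at the follow-up visit whenever that takes place, and the four-week remark in 8.3.1 is only loose wording. Even then the time left after the injection is 0 days. The lack of observation after penicillin therefore depends neither on d nor on how many patients are referred.

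**Step 4. The two penicillin criteria for an unhealed lesion.**

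| Azithromycin status | 4.7 (unhealed) | 8.4 (suspected failure) |
|---|---|---|
| Taken about four weeks earlier | swab, offer penicillin | offer penicillin if failure is suspected |
| Not taken | swab, offer penicillin | no failure to suspect; action not stated |

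The protocol text names no check at the visit that azithromycin was taken, or when. The case report form (Appendix B) is not in the documents and may record it.

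**The case against.** The strongest reply is that sections 4.7, 8.1 and 8.4 should be read together. Two of them time the visit from treatment, and 8.4 limits penicillin to suspected failure, so the visit presupposes that treatment was given. The only count from enrolment sits inside an AE definition, not a visit schedule. Section 8.1.1 also lists treatment with screening, enrolment and sample collection among activities mostly done outdoors in the community, which suggests that much dosing happens at or near enrolment. The allergy-history check reduces the risk from penicillin. The study is observational and offers guideline care.

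Much of this stands. It makes the untreated patient a possible case, not an expected one. It does not make the starting points agree, because referral remains open in 4.7 and is the only route named in 8.2. Nor does it add any AE observation after penicillin: the history check lowers the chance of a reaction but does not record one.

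A reader might infer four stronger claims that the documents do not support.

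- *Many untreated people will be given penicillin.* No share referred, untreated or unhealed is given, so any count would be invented. The azithromycin offer in 4.7 has no time limit and could be read as still open at week four.
- *Serious penicillin reactions cannot be reported.* The SAE definition has no window and 8.3.2 gives a reporting route, so an SAE may still be reportable. What is missing is a planned contact or a stated passive route by which the study would hear of it.
- *Untreated infection cannot be told from new macrolide resistance.* Section 6.6 plans sequence comparison with reference strains, which can show a candidate mutation without a treatment date, and Appendix B may hold that date.
- *The main results are at risk.* Section 4.7 places all samples for the primary analysis at the first visit.

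**Conclusion.** The point holds as a timing and safety-capture defect. Sections 8.1 and 8.4 conflict with 8.3.1 unless azithromycin is taken on the enrolment day, and the text does not require that. After penicillin, at most the day of the visit remains in the AE window. If the visit is timed from treatment taken d days after enrolment, the injection falls d days after the four-week limit. The zero-day result rests on the text alone; the d-day result assumes some delay, whose length and frequency are unknown.

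The mismatch between an unhealed lesion in 4.7 and suspected failure in 8.4 is also real, but its reach cannot be sized from the documents. The LAMP accuracy and risk-factor analyses do not change. The correction is cheap and should be made, because it governs a treatment decision and the recording of the one serious reaction that the protocol anticipates.

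**What to change.** 1. In 4.7, 8.1, 8.3.1 and 8.4, time the visit from the date azithromycin was taken. Record that date, or that it was not taken, on the case report form if it is not already there.
2. In 4.7, use the 8.4 criterion: offer penicillin for suspected failure after azithromycin. If azithromycin was not taken, give it and rebook the review four weeks later.
3. In 8.3.1, extend the AE window for a stated period after any penicillin, for example 7 days, and give the participant or guardian a stated way to report a reaction. With this rule 7 days of window follow the injection whatever the value of d.
4. In 8.4, correct the cross-reference from 5.6 to 4.7.

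The cost is wording in four sections, at most one form item, an occasional rebooked visit, and a passive reporting route with no added scheduled contact. The amendment would go to the sponsor's ethics committee and the three national committees named in section 12. Sample size and the planned LAMP and risk-factor analyses stay as they are.

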#### **4.8 Data Analysis**

Quantitative data analysis will be performed with R, STATA and other software packages. Initially we will perform univariable logistic regression analyses on each potential risk factor. If any factors are found to be associated with yaws we will include these in multivariate logistic regression models with age and gender included *a priori* in order to calculate odds ratio for any factors associated with active yaws. We will also calculate the 95% confidence interval for each odds ratio. The multivariate analysis will allow us to determine the strength of associations between active yaws and each factor, or combinations of factors. All statistical analysis will be performed to the 95% significance level. For the Luminex assay, we will use appropriate statistical tools and published literature to determine cut-off values for each antibody and calculate seroprevalence with 95% confidence intervals.

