#### **1.8 Primary objectives:**

- 1) Perform active case searching and collect household and community level data to identify risk factors associated with yaws transmission and disease.
- 2) Assess the accuracy, acceptability and feasibility of the TPHD-LAMP assay for *T. pallidum* and *H. ducreyi* diagnosis under programmatic conditions in yaws endemic areas in Ghana, Cote d'Ivoire and Cameroon to determine its suitability as a diagnostic in yaws eradication programmes.
- 3) Testing the *Treponema pallidum* macrolide resistance (TPMR)-LAMP assay in a field setting.

- 4) Establish other infectious causes of non-yaws ulcers using specific PCR tests and next generation sequencing techniques, including novel devices such as employing the Minion for nanopore sequencing.
- 5) Collect data on community, patient and healthcare worker knowledge, attitudes and practices in relation to yaws.
- 6) Determine the acceptability and feasibility and cost effectiveness of the TPHD-LAMP assay.

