### 3.2 Study Sites

In each of the three countries, national reporting data will be used to select at least three districts that are highly endemic for yaws, facilitating rapid fulfilment of the sample size required number of yaws cases for the diagnostic accuracy study. The number of villages/communities selected will depend on prevalence of the disease. This exercise will be conducted with the yaws programme national coordinators in the three endemic countries.

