### 3.3 Consent and information for participants

In each site we will conduct active case finding activities in collaboration with Ministry of Health departments and National Yaws Programmes. For sub-studies 1-3, all residents in selected communities will be eligible to participate in the study. Prior to any study procedures, written informed consent will be obtained from participants or, from parents, guardians, or legal

representatives if the participant is under the age of consent. Following national recommendations informed consent will be conducted in English or French, with the assistance of a community representative translating if necessary. If a person is illiterate the study information and consent procedure will be clearly explained to them by a member of the study team or a local translator. If a translator is used they will be required to witness the informed consent procedure. Children and minors over ten years of age and under the age of consent, will also be required to give verbal assent for enrolment. If consent is not given for future research, it will be indicated under the appropriate section in the consent form. If any participants wishes to withdraw from the study at any point post-enrolment this will be indicated to study coordinator and data managers for complete elimination of that participants information. Consent forms, approved by all relevant ethical review boards, will be available in English and French, as appropriate. Individuals at each site will be consented for participation into each sub-study based on the relevant inclusion/exclusion criteria (see sections: 4.2; 5.2; 6.2; 7.2).

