### 4.3 Sample Size Considerations

We aim to screen approximately 60,000 individuals, 20,000 in each country. Of these we estimate 6000 individuals will present with yaws like lesions and 600 will have active yaws (i.e. present with yaw-like lesions and confirmed serologically). The remaining participants will be classed as either negative for yaws due to the absence of clinical signs or negative serology or suspected latent yaws if sero-reactive. We will aim to enrol all 6000 participants with yaws like lesions and a further 6000 without clinical yaws into this sub study. This will give us >80% power to detect risk factors associated with yaws with an odds ratio of 3. If resources allow, we will collect dried blood spots of half of the people enrolled into sub-study 1 giving us roughly 6000 dried blood spots samples. This would allow us to detect 5% seroprevalence with 0.5% precision, and a seroprevalence of 50% with a precision of 1.3%, which is deemed more than sufficient for a convenience sample .

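### The risk-factor regression in section 4.8 ignores clustering by community and household and has no country or district term, so intervals for shared exposures would be too narrow and country differences could pass as risk factors

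*Combined protocol and SAP*

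**What the plan says.** Section 4.8 holds the whole risk-factor analysis. The first step is stated as "Initially we will perform univariable logistic regression analyses on each potential risk factor". The second, with two covariates fixed in advance, is "If any factors are found to be associated with yaws we will include these in multivariate logistic regression models with age and gender included". A 95% confidence interval is to be given for each odds ratio. No random effect, generalised estimating equation (GEE), robust variance or stratification is named, and no country, district, community or household term.

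The design is nested. In each of the three countries, "national reporting data will be used to select at least three districts that are highly endemic for yaws" (section 3.2). Below district, "The number of villages/communities selected will depend on prevalence of the disease", so the number of communities is open. Within them, "all residents in selected communities will be eligible to participate in the study" (section 3.3).

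The exposures of interest sit partly at the shared levels. Primary objective 1 in section 1.8 is "Perform active case searching and collect household and community level data to identify risk factors associated with yaws transmission and disease".

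On numbers, section 4.3 states "We will aim to enrol all 6000 participants with yaws like lesions and a further 6000 without clinical yaws into this sub study", expects 600 with active yaws, and claims more than 80% power for an odds ratio of 3. For about 6,000 dried blood spots it says "This would allow us to detect 5% seroprevalence with 0.5% precision, and a seroprevalence of 50% with a precision of 1.3" per cent.

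**The concern.** Yaws is transmissible, so people in the same community or household are likely to have correlated outcomes. When the exposure is also shared at that level, ordinary logistic regression counts each person as independent information about it and understates the standard error. Two things follow. Intervals for community-level factors are too narrow. And because the univariable step selects factors using the same standard errors, spurious factors pass into the multivariable model.

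The missing country and district term is a separate problem. If both an exposure and the ratio of cases to comparison participants differ between countries, pooling produces an association that exists within none of them. Adjusting for age and gender does not remove it.

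At stake is the inference for a listed primary objective, which section 2.1.4 links to better case searching and contact tracing.

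**Working it through.** **1. The plan's own precision figures (section 4.3).** With 6,000 samples and simple random sampling, half-width = 1.96 × √(p(1−p)/6000).
- p = 5%: 1.96 × √(0.05 × 0.95/6000) = 0.55% (stated 0.5%).
- p = 50%: 1.96 × √(0.25/6000) = 1.27% (stated 1.3%).

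These match a design effect of about 1, so this other calculation for the same population also assumes independence.

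**2. Inputs for the regression.** From section 4.3: 600 active cases and 6,000 lesion-free participants (6,600 analysed), or 600 against all 11,400 other enrolled participants (12,000 analysed); section 4.8 does not say which. Assumed, because the documents do not give them: 50 to 200 communities, hence m = 6,600/200 = 33 to 12,000/50 = 240 analysed per community; ICC 0.01 to 0.05; two-sided 5% tests.

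**3. Community-level exposure.** Design effect D = 1 + (m−1) × ICC. True type I error = 2 × (1 − Φ(1.96/√D)).

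| ICC | D at m = 33 | Type I error | D at m = 240 | Type I error |
|---|---|---|---|---|
| 0.01 | 1.32 | 9% | 3.39 | 29% |
| 0.02 | 1.64 | 13% | 5.78 | 42% |
| 0.05 | 2.60 | 22% | 12.95 | 59% |

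The correct interval (log-odds scale) is √D times as wide: from √1.32 = 1.15 to √12.95 = 3.6 times.

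**4. Household exposure, same formula.** With 1 to 2 enrolled per household and ICC 0.1 to 0.3, D is 1.0 to 1.3 and the error 5% to 9%. With 5 per household and ICC 0.3, D = 1 + 4 × 0.3 = 2.2 and the error is 19%.

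**5. Simulation.** Settings: 60,000 screened, 1% active yaws, 10% of the others enrolled, community log-odds SD 0.5 (ICC about 0.02 in the analysed sample), a null exposure assigned to half the communities, 4,000 replicates per setting.

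| Communities | Plain logistic | Community-robust |
|---|---|---|
| 50 | 33% | 7% |
| 100 | 22% | 6% |
| 200 | 13% | 5% |

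For an individual-level exposure unrelated to community, plain regression stayed at about 5%.

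**6. Country confounding.** Assume 20,000 screened per country (section 4.3) and active yaws of 0.5%, 1.0% and 1.5%, giving 100, 200 and 300 cases, with 2,000 lesion-free participants enrolled per country and no association within any country.
- Exposure 20/30/40%: exposed cases 20 + 60 + 120 = 200 of 600; exposed comparison 400 + 600 + 800 = 1,800 of 6,000. Pooled odds ratio = (200 × 4,200)/(400 × 1,800) = 1.17 (95% CI 0.98 to 1.39).
- Exposure 10/30/50%: exposed cases 10 + 60 + 150 = 220; exposed comparison again 1,800. Pooled odds ratio = (220 × 4,200)/(380 × 1,800) = 1.35 (1.13 to 1.61).
- Equal cases per country: the false odds ratio is 1.00.

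**7. Power for an odds ratio of 3.** Two-proportion formula with both group sizes divided by D. The stated power cannot be reproduced exactly, because no exposure prevalence is given. The smallest prevalence in the comparison group that gives 80% power is 0.6% at D = 1, 1.4% at D = 2.3 and 5% at D = 7.6 (600 v 6,000), and 9% at D = 13 (600 v 11,400).

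**The case against.** Section 4.8 does not state a variance estimator, so its silence might leave room for a cluster-adjusted fit. But it does set out a concrete method and the covariates to be forced in. An analyst following it would fit the plain model, and nothing elsewhere in the supplied text adds an adjustment. Location enters a regression only for the sub-study 4 questionnaires (section 7.4).

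The questionnaires in Appendices A and B are not in the text reviewed, so location or household variables may be collected and could be candidate factors. That is fair. They would then enter only through univariable screening, and a covariate chosen that way would not correct the standard errors of community-level exposures.

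The sizes depend on an assumed ICC and number of communities, and the largest concern exposures constant within a whole community. This stands: the figures are illustrations, and individual-level factors, or household factors with few enrolled per household, are much less affected.

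The country bias needs both exposure and case ratio to differ by country, and one of the two illustrated intervals includes 1. Sampling the lesion-free group in proportion to cases would remove it, but the plan does not say how that group is sampled. It is a possibility, secondary to the variance problem.

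The blood-spot precision statement concerns a convenience sample and does not show how section 4.8 will be fitted. It is supporting evidence only.

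Finally, section 1.7 makes the LAMP assay's suitability the main aim, with risk factors as supporting work. Section 1.8 nevertheless lists risk factors as the first primary objective.

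**Conclusion.** The concern holds and should be fixed before analysis. As written, the plan gives over-narrow intervals and excess false positives for exposures shared within communities: a true type I error of about 9% to 59% for a nominal 5%, over 50 to 200 communities and ICCs of 0.01 to 0.05. Even the mild end exceeds the nominal level. The direction requires only a positive ICC, which is plausible for a transmissible disease; the size cannot be fixed from the documents. Country differences could also appear as risk factors. The harm is to interval coverage and factor selection. The claim of more than 80% power for an odds ratio of 3 survives moderate clustering for all but rare exposures.

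**What to change.** In section 4.8:
- Specify one primary method: either mixed-effects logistic regression with a community random intercept (plus household where several members enrol), or GEE or cluster-robust standard errors at community level, with a small-sample correction if communities are few. The first estimates conditional odds ratios and the second marginal ones, so the text should say which is reported.
- Apply it to both the univariable and the multivariable steps. Univariable screening can stay if it uses the adjusted standard errors.
- Include country or district as a fixed effect alongside age and gender.
- State which participants form the comparison group.
- Confirm that community and household identifiers are recorded for every enrolled participant. Without them the problem may not be repairable at analysis.

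The seroprevalence intervals should be cluster-adjusted in the same way.

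The cost is analysis wording and one line on identifiers, with no change to recruitment or sample size. Intervals will be wider, correctly so. Exposures that vary only between districts cannot be estimated if district is a fixed effect; use country for those.
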